## 7.2 Programming Conventions

Unless stated otherwise, the term “descriptive statistics” refers to the number of subjects (n), mean, median, standard deviation, minimum, and maximum for continuous variables and frequencies and percentages for categorical variables.

Unless specified otherwise, the denominator for percentages for categorical data will be based on the number of subjects or observations with nonmissing data appropriate for summary purposes. The denominator for percentages for incidence data (such as adverse events) will be based on the number of subjects in the analysis population “at risk”.

Minimum and maximum values will be presented at the precision of the original value, means, medians will be rounded to 1 decimal place greater than the precision of the original value, standard deviations and standard errors will be rounded to 2 decimal places greater than the precision of the original value. Percentages will be rounded to 1 decimal place. Percentages that round down to 0 or up to 100% will be displayed as “< 0.1%” and “> 99.9%”, respectively.

All summary tables will be presented by treatment group displayed as AR101 and placebo. For disposition, demographic, and other summaries of baseline and history data, a total column for both treatment groups combined will be included.

All relevant data collected in the database will be included in data listings and sorted by treatment group, subject number, and visit and time point as appropriate. The treatment group will be displayed by AR101 then placebo.

Unscheduled visits will be listed but not included in by-visit summaries. Results from unscheduled visits may be used as baseline values and for other derivations not tied to visit names (for example, unscheduled visits are included in the determination of worst postbaseline values for laboratory shift tables).

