6.4 Unscheduled Visits / Unscheduled Blood Draws

The procedures performed at unscheduled visits may include any or all of those performed at up-dosing visits as well as PEES v2.0 questionnaire.

Subjects waiting for activation of follow-on protocols before completing their final exit visit procedures (treatment unblinding, FAQLQ, and FAIM) will continue blinded treatment and have an unscheduled visit every 4 weeks or sooner until all conditions are met for exiting the study. All exit visit procedures will be considered completed at the final unscheduled visit when unblinding, FAQLQ, and FAIM are completed. If the final unscheduled visit is more than 6 weeks after the scheduled exit visit, all exit visit procedures must be repeated. Additionally, laboratory evaluations must be repeated for subjects who exit the study > 6 weeks after the 300 mg visit, and these will serve as the screening/baseline values for the follow-on studies as applicable. Subjects will then enroll in the appropriate follow-on study based on their treatment assignment.

Additionally, if a subject or parent/guardian declares the intention to discontinue IP dosing, whether at a scheduled visit or an unscheduled visit, a blood draw should be performed to obtain a CBC, immunoglobulin assays, and optional blood and/or saliva samples (if the subject is participating in the sub-study). If a blood draw is performed at this time, it will take the place of the Exit Visit/Early Discontinuation Visit blood draw (Section 6.3.6).

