## 7 DEFINITIONS, DERIVATIONS, AND CONVENTIONS

### 7.1 Definitions and Derivations

- Study day is calculated as (assessment date – first dose date + 1) for assessments and visits performed on or after the first dose date, and (assessment date – first dose date) for assessments and visits prior to the first dose date.
- Baseline is defined as the last nonmissing value prior to the first dose of randomized study treatment in ARC007.
- Change from baseline is calculated as the observed value after the first dose – baseline value.
- The screening period is defined as the time beginning with the date and time of informed consent through the day prior to randomization.
- Initial escalation is defined as the time beginning with the date and time of the first dose of randomized study product at the study site and ending with the date of the last dose of randomized study product taken prior to up-dosing.
- Up-dosing is defined as the time beginning with the date and time of the first dose of study product at 3 mg at home, and ending with the date and time of first dose at

300 mg at the study site. Up-dosing will be approximately 20 weeks in duration, but may be extended to a maximum of 40 weeks to accommodate dose reductions and re-escalations, if necessary.

- A 300 mg QD period will be defined as the time beginning with the date and time of the first dose of study product at 300 mg at home and ending with the date of the last dose of study product. This period will be ideally approximately 2 weeks in duration at the end of ARC007, but dosing may continue up to a maximum of 48 weeks after day 1 to ensure tolerability of 300 mg prior to exiting ARC007. Some subjects continued to receive 300 mg doses in ARC007 after the expected rollover date while waiting for activation of ARC008 or ARC011 at the study site. The 300 mg doses as a result of the rollover delay will be included in the 300 mg QD period.

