## 7.2.2 Visit Windows

All information will be listed, summarized, and analyzed according to the nominal visit time point, study period, or dose. No visit windowing will be performed.

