#### **9.8.12 Quality of Life Assessments (FAQLQ and FAIM)**

Quality of life assessment using the FAQLQ and the FAIM will be performed at the baseline and exit visit in ARC007.

Separate FAQLQ and FAIM instruments are administered based on age group. Parent/caregiver versions are also administered for subjects who are aged 17 years or younger. Due to differences between the various instruments, separate summaries will be provided by age group and person who completed the questionnaire (subject or parent/caregiver).

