### FAQLQ

The FAQLQ is a self-report instrument intended to assess the effect of food allergy on the subject's quality of life. Evaluations are done by the subject using a different form by age group (8-12 years and 13-17 years) ([Flokstra-de Blok, 2008](#); [Flokstra-de Blok 2009](#)). Evaluations are also done by the parent/caregiver using a different form by age group (4-6 years, 7-12 years, and 13-17 years) ([DunnGalvin, 2008](#)).

Each question is scored from 1 to 7. The number of items and domains varies by instrument administered. For reporting, the domains for each included form are as follows:

Teen form –

- a) Allergen Avoidance and Dietary Restrictions
- b) Risk of Accidental Exposure
- c) Emotional Impact

Child form –

- a) Allergen Avoidance and Dietary Restrictions (Allergen Avoidance + Dietary Restrictions)
- b) Risk of Accidental Exposure
- c) Emotional Impact

Parent form teen –

- a) Social and Dietary Limitations (Dietary Restrictions + Social Restrictions)
- b) Food Anxiety
- c) Emotional Impact

Parent form 7-12 –

- a) Social and Dietary Limitations
- b) Food Anxiety
- c) Emotional Impact

Parent form 4-6 –

- a) Social and Dietary Limitations
- b) Food Anxiety
- c) Emotional Impact

For each domain, the domain average score is the arithmetic average of the non-missing items comprising the domain. For all forms, the total score will be calculated as the average of the domain averages: (average a + average b + average c) / 3. For FAQLQ-PF 4-6, if items are completed that were not included for this age group, these items will not be included towards the scoring.

Descriptive statistics and scores of total and domain scores along with their changes from baseline will be provided. Data will be summarized separately by age group and responder (subject or parent/caregiver).

Listing of the raw scores as recorded in the case report form will be provided, sorted by treatment group and subject identification (ID).

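### Exit FAQLQ/FAIM of subjects whose exit is delayed are collected at an unscheduled visit, and no SAP rule brings them into the change-from-baseline summary

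*SAP*

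**What the plan says.** **Protocol.** Under Section 6.3.6, a subject who tolerates 300 mg for two weeks has an Exit Visit. Unblinding, FAQLQ and FAIM are held back until ARC008 and ARC011 are both open at the site, open-label product is on hand and the major queries are closed. Until then the subject stays on blinded treatment with unscheduled visits at least every 4 weeks. Section 6.4, repeated in Appendix 1 footnote c, closes the sequence: "All exit visit procedures will be considered completed at the final unscheduled visit when unblinding, FAQLQ, and FAIM are completed". The Appendix 1 schedule accordingly marks FAQLQ/FAIM in the Unscheduled Visit column as well as the Exit Visit column.

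**SAP.** Section 7.2: "Unscheduled visits will be listed but not included in by-visit summaries". Section 7.2.2 applies nominal visit, period or dose to all information and adds "No visit windowing will be performed". Section 9.8.12: "Quality of life assessment using the FAQLQ and the FAIM will be performed at the baseline and exit visit in ARC007". The FAQLQ subsection continues: "Descriptive statistics and scores of total and domain scores along with their changes from baseline will be provided". The FAIM subsection has the equivalent for its items and total.

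The SAP was written knowing that delays had happened. Section 7.1 records: "Some subjects continued to receive 300 mg doses in ARC007 after the expected rollover date while waiting for activation". It assigns those extra doses to the 300 mg QD period. It has no matching rule for questionnaires completed at the end of the wait.

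**The concern.** The protocol treats the deferred questionnaire as the planned exit measurement, while the SAP's general rule treats anything from an unscheduled visit as incidental. If a programmer follows the SAP as written, data that were planned and collected are left out of the summary they were collected for, and no other post-baseline FAQLQ/FAIM record can replace them for a completer.

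The omission would not be random across the trial. It would fall on subjects who reached the end of dosing before their site was ready to roll them over, so it would follow site start-up and query handling. FAQLQ and FAIM are also reported separately by age form and by respondent, so any loss comes out of tables that are already subdivided.

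**Working it through.** No sample size, power or alpha figure bears on this point, so the check is mainly a reading of the two documents side by side, followed by simple arithmetic on the possible size.

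**Step 1. What is deferred.** Section 6.3.6 speaks at first of questionnaires in general. Its own sub-bullet and Section 6.4 then name the items: unblinding, FAQLQ and FAIM. ACT, TNSS, SPT, PEFR and vital signs are not named and stay at the scheduled Exit Visit.

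**Step 2. When other procedures are repeated.** Time is counted from the first 300 mg visit.
- Scheduled exit: 2 weeks (Appendix 1).
- Laboratory repeat: beyond 6 weeks (Section 6.4).
- Repeat of all exit procedures: more than 6 weeks after the scheduled exit, so beyond 2 + 6 = 8 weeks.

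A repeat therefore always follows a scheduled Exit Visit value, which remains in the by-visit tables. Haematology and immunoglobulins are summarised at the 300 mg visit (SAP Sections 9.8.9 and 9.8.17), which is also scheduled. Loss of scheduled-exit ACT, SPT, TNSS, PEFR and vital-sign values under the rule: 0.

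**Step 3. What happens to the deferred FAQLQ/FAIM.**
- Visit at which they are collected: unscheduled (protocol 6.4).
- Visits the SAP expects: baseline and exit (9.8.12).
- Visit reassignment: none (7.2.2).
- Treatment of unscheduled visits: listings only (7.2).

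Taken together, the delayed completer contributes a baseline value and no exit value.

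**Step 4. Possible size.** The documents give no count of delayed subjects. Let f be the delayed share of completers. The standard error of a mean is SD/√n. With n(1 − f) subjects left and the same SD, it is multiplied by 1/√(1 − f). For subject counts, the only planning figure is up to 500 randomised 2:1, that is 500 × 2/3 ≈ 333 AR101 and 167 placebo. Using these as if everyone completed gives an upper bound.

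| Assumed f | AR101 left out (333 × f) | Placebo left out (167 × f) | SE multiplier |
|---|---|---|---|
| 10% | 33 | 17 | 1/√0.90 = 1.05 |
| 25% | 83 | 42 | 1/√0.75 = 1.15 |
| 50% | 166.5 (half the arm) | 83.5 (half the arm) | 1/√0.50 = 1.41 |

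Every value of f here is an assumption. The multiplier applies equally within any age-form or respondent table if f is the same there.

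**The case against.** The best reply is that exclusion is only one reading.
- The rule in SAP Section 7.2 concerns by-visit summaries. Sections 9.8.8 (ACT), 9.8.11 (TNSS) and 9.8.15 (PEFR) specify presentation by visit, whereas the FAQLQ and FAIM text specifies age group and respondent.
- Section 7.1 names no visit: "Change from baseline is calculated as the observed value after the first dose – baseline value".
- Section 7.2 has an exception: "Results from unscheduled visits may be used as baseline values and for other derivations not tied to visit names".
- The protocol regards the final unscheduled visit as completing exit, and the case report form may store the questionnaires under an Exit label.

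This stands to the extent that the loss is not certain. It does not remove the gap. Section 7.2.2 covers all information, Section 9.8.12 ties these instruments to a named visit, and the example given for the exception is a worst postbaseline laboratory value, which is a different kind of derivation. The documents do not show how the forms are labelled, so inclusion would depend on a choice that the SAP should state.

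Three stronger readings are tempting and should not be drawn:
- *All exit data of delayed subjects disappear.* They do not. Steps 1 and 2 show that only FAQLQ/FAIM are deferred and that only later repeats of other procedures are left out.
- *A subject count can be given.* A reader might apply the ARC001 completion rate and an assumed 30% delay: 333 × 23/29 ≈ 264, and 264 × 0.30 ≈ 79 AR101 subjects. The 30% has no source, and the rate comes from a 29-subject arm in a trial that also had a maintenance period and an exit food challenge. Nor is every completer at a slow site affected: only those who finished before the exit conditions were met.
- *The treatment contrast is biased.* Both follow-on protocols must be open whichever arm the subject is in, and assignment is still blinded during the wait. The documents show no selection by arm, and no between-group test is planned.

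**Conclusion.** The point holds for FAQLQ and FAIM only. Followed literally, the SAP omits from the summary the single planned post-baseline questionnaire of each completer whose exit was delayed. The SAP establishes that there were such subjects but not how many, so the proportion lost is unknown and equals the delayed share of completers. The 1.05 to 1.41 range for the standard error illustrates an assumed 10% to 50%. It is not an estimate.

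The conclusion rests on the forms being recorded under an unscheduled visit, as the protocol describes, and on SAP Sections 7.2 and 7.2.2 applying to them. The importance is that of an exploratory, descriptive endpoint. Raw scores are listed in any case, so nothing is irrecoverable. It is still worth correcting, because a stated rule would discard data gathered as planned and the remedy is trivial.

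**What to change.** Add one sentence to SAP Section 7.2 or 9.8.12: FAQLQ and FAIM completed at the final unscheduled visit, when the subject is unblinded, are analysed as the exit assessment and enter the change-from-baseline summaries. Limit the mapping to these two instruments. If the whole visit were relabelled as Exit, subjects delayed by more than 6 weeks would have two exit records for procedures such as SPT and ACT, and the SAP has no rule for choosing between them.

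Show weeks from baseline to the exit questionnaire alongside the scores. The cost is a sentence and a visit-mapping rule, with no new data and no protocol change. The one drawback is that the exit assessment then spans a wider range of time on treatment, which the weeks-from-baseline display makes visible.

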### 7.2.1 Rules for Missing Data

All adverse events with partial/missing dates and times will be considered treatment-emergent adverse events unless a partial date clearly indicates that it occurred

before the first dose of study treatment. All therapies with partial or missing dates and times recorded on the concomitant medication or non-drug therapy case report form pages will be considered concomitant unless a partial stop date and time clearly indicates it was stopped prior to the first dose of study treatment. Start and stop dates will be imputed when partial dates are present as needed to determine treatment-emergent events and concomitant medications. No imputation will be done for a completely missing start/stop date or for subjects who did not receive study treatment.

Start dates with a missing day but with month and year populated will be imputed such that:

- If the provided month and year match the month and year for that subject's first dose date, then the first dose date will be used
- In all other cases the first day of the month will be used with the provided month and year

Start dates with a missing day and month with year populated will be imputed such that:

- If the provided year matches the year for that subject's first dose date, then the first dose date will be used
- In all other cases, January 1 will be used with the provided year

Stop dates will be imputed as follows:

- Missing day with a provided year and month will use the last day of the month
- Missing day and month with provided year will use December 31

If the imputed stop date is greater than the last study date for the subject, then the imputed date will be replaced with the last known subject date.

The reported date of the reaction on the peanut allergy history case report form page and date of diagnosis of peanut allergy will be imputed when the month or day is missing as follows:

- Missing day is set to 1 if the same year and month as the informed consent date. Otherwise it is set to 15
- Missing month and day are set to January 1 if the same year as the informed consent date. Otherwise it is set to July 1.

No imputations will be made for other missing data unless specified otherwise.

## 7.2.2 Visit Windows

All information will be listed, summarized, and analyzed according to the nominal visit time point, study period, or dose. No visit windowing will be performed.

## 8 TIMING OF ANALYSIS

Analyses for data safety and monitoring committee (DSMC) review were planned to occur approximately every 3 months to monitor safety.

The final analysis of safety will be performed after all subjects complete exit/early termination visit assessments in ARC007. Subjects who received AR101 and completed

ARC007 have the option to participate in the ARC011, an open-label safety extension study to evaluate the safety and tolerability of AR101 300 mg/day maintenance treatment for up to 6 months.

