Beginning at signed informed consent and assent as age-appropriate, all AEs will be evaluated from the onset of the event until the time the event is resolved or medically stable, or until 30 days after the Exit or Early Discontinuation Visit, whichever comes first, with the exception of GI AEs, detailed further below. Adverse events ongoing at the time that study treatment is discontinued may not be determined to be medically stable until 30 days after the Exit or Early Discontinuation Visit has been conducted, in which case additional visits after the Exit or Early Discontinuation Visit may be required. Subjects who discontinue dosing prematurely due to chronic/recurrent GI AEs will complete the Pediatric Eosinophilic Esophagitis Symptom Score (PEESS™ version 2.0) questionnaire and return to the clinic for evaluation monthly for at least 6 months (if the subject is asymptomatic, telephone follow-up with an Investigator may substitute for in-clinic visit, at the Investigator's discretion). If chronic/recurrent GI AEs persist beyond 6 months, subjects are to continue to be followed with monthly clinic visits (telephone follow-up with an Investigator may substitute for in-clinic visit, at the Investigator's discretion) until the symptoms have resolved or are assessed to have stabilized with optimal medical management or the Investigator deems them to be irreversible. The protocol provides additional specific guidance about symptomatic medical management and referrals to a gastroenterologist, as necessary, in Section 7.3.4.2. Treatment will be administered in a double-blind fashion.

A DSMC has been established to monitor the study for safety.

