6.8 Visit Windows

Strict adherence to the dosing schedule should be maintained:

- Study visits should occur within a \pm 2-day window of the scheduled visit date (ie, 2 days before or 2 days after the scheduled visit date)
- The Early Discontinuation Visit is to occur 14 days after the last dose of IP where IP dosing has been ceased for reasons other than study completion. The permissible window is minus 3 days to plus 7 days.

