7.3.4.2 Gastrointestinal AE Resulting in Prolonged Disruption of Dosing (GI AEIs)

Gastrointestinal AEs, typically chronic/recurrent GI AEs, that result in a prolonged disruption of dosing will be considered AEIs and will be assessed longitudinally according to the procedures described below. For the purpose of delineating these AEIs, prolonged disruption of dosing is defined as withholding IP for > 7 days. This will include 3 categories of subjects:

- Any subject whose dose is withheld for > 7 days due to GI AEs and resumes dosing at a reduced dose level
- Any subject who develops chronic/recurrent GI AEs at or before reaching the 20-mg dose level and resumes dosing after a 30-day dosing hiatus
- Any subject who permanently discontinues dosing who had experienced GI AEs (Section 4.3.1).

All subjects who fall into any of these 3 categories will be asked to fill out the PEESS v2.0 questionnaire (Franciosi et al, 2011), with the assistance of a parent/ guardian, as appropriate, every month for 6 months. However, it should be noted that the PEESS v2.0 was not designed to establish a diagnosis of EoE, and has not been validated for use in subjects with GI symptoms of other etiologies. Furthermore, the discriminant validity of the questionnaire has not been reported in either longitudinal natural history or interventional studies. For these reasons, the use of the PEESS v2.0 to monitor the clinical course of GI symptoms must be considered exploratory. Nevertheless, the PEESS v2.0 has shown good content and construct validity for all subjects (Franciosi et al, 2011; Martin et al, 2015), and so holds promise for being a valuable tool to follow the clinical course of EoE or an EoE-like immune-mediated GI syndrome. Thus, the PEESS v2.0, could reveal trends toward symptomatic improvement or worsening that might otherwise go undetected.

Subjects who discontinue dosing prematurely due to chronic/recurrent GI AEs will be asked to return to the clinic for evaluation monthly for \geq 6 months (if the subject is asymptomatic, telephone follow-up with the Investigator may substitute for in-clinic visit, at the Investigator's discretion). If chronic/recurrent GI AEs persist beyond 6 months, subjects are to be followed with monthly clinic visits (telephone follow-up with an Investigator may substitute for in-clinic visit, at the Investigator's discretion) until the symptoms have resolved or are assessed to have stabilized with optimal medical management.

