9. STATISTICAL CONSIDERATIONS

This protocol outlines the major statistical considerations for the ARC007 study. Full details on the statistical methodology to be used in the analysis and data handling for this trial will be described in the statistical analysis plan (SAP) to be developed prior to database lock and statistical analysis.

Data will be summarized using descriptive statistics within treatment group. No specific hypothesis testing or comparisons between the treatment groups are planned for this study.

Details of within-group comparisons relative to baseline values and any exploratory comparisons between groups will be described in the SAP.

Descriptive statistics will be presented in the following manner:

- Continuous data (ie, age, body weight, and height) will be summarized descriptively by mean, standard deviation, median, and range.
- Categorical data (ie, sex and race) will be presented as enumerations and percentages.

Data will be summarized by treatment group and treatment phase.

Data will be summarized in tables for each treatment group, treatment groups combined, and treatment phase.

Data will be listed for each subject.

The end of study is defined as the date of the last visit of the last subject.

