### **9.8.2 GI Adverse Events**

Of subjects who discontinue due to chronic/recurrent GI adverse events, GI adverse events will be summarized by preferred term, study period, age group (4-11 years, 12-17 years, 4-17 years) and treatment group (AR101, placebo). Additionally, any of these subjects whose GI adverse events were ongoing will be further summarized as having events resolved prior to 2, between 2 and 4, between 4 and 12, and  $\geq$  12 weeks following cessation of dosing. Summaries will be provided using the safety population by age group (4-11 years, 12-17 years, 4-17 years) and treatment group (AR101, placebo).

All reported GI treatment-emergent adverse events for subjects who discontinue the study early due to chronic/recurrent GI AEs will be listed by age group, treatment group, subject, study period, and event and will include weeks to resolution following cessation of dosing for events that were ongoing.

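### The SAP's GI-resolution table has no row for unresolved events, no fixed denominator and no data cut-off, and may be run before GI follow-up ends

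*SAP*

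**What the plan says.** **Endpoint and table.** SAP 4.2 defines the endpoint among subjects who leave early because of chronic or recurrent GI adverse events. SAP 9.8.2 says that those whose events were ongoing "will be further summarized as having events resolved prior to 2, between 2 and 4, between 4 and 12", with a fourth class of 12 weeks or more. Neither section has a class for events that are unresolved, stable or of unknown outcome.

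**Denominator.** SAP 9.8.2 states none for this table. SAP 7.2 sets a default, subject to other specification: "the denominator for percentages for categorical data will be based on the number of subjects or observations with nonmissing data". It has a separate at-risk rule for incidence data. SAP 7.2.1 does not impute a completely missing stop date.

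**Timing.** SAP 8: "The final analysis of safety will be performed after all subjects complete exit/early termination visit assessments in ARC007". For a dropout, Protocol 6.8 says: "The Early Discontinuation Visit is to occur 14 days after the last dose of IP". It adds: "The permissible window is minus 3 days to plus 7 days".

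**Follow-up.** Under Protocol 3, subjects who stop for these events "return to the clinic for evaluation monthly for at least 6 months". Protocol 7.3.4.2 goes further: "If chronic/recurrent GI AEs persist beyond 6 months, subjects are to be followed with monthly clinic visits". Follow-up then ends at resolution or stabilization; Protocol 3 adds a judgement by the investigator that the symptoms are irreversible.

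**The concern.** The protocol names three ways for a GI event to end follow-up: resolved, stabilized or irreversible. The SAP table has room only for the first. A subject who is still symptomatic at last contact has no resolution time and no row. The SAP does not say whether that subject stays in the denominator.

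The analysis trigger is tied to a visit about 2 weeks after the last dose, whereas the endpoint needs status at 4 and 12 weeks and the protocol follows these subjects for 6 months or more. A subject who stops shortly before the trigger can enter the table before that status exists.

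Of the endpoints listed in SAP 4, this is the only one on whether GI harm reverses after dosing stops. Protocol 1.4.1 says that eosinophilic esophagitis is thought to be reversible on stopping, so a reader will look to this table for evidence. A table that cannot show non-resolution, or that shows it only as an unlabelled gap, does not answer the question.

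**Working it through.** The plan gives no figure to reproduce.

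**1. Calendar.** The Early Discontinuation Visit is at day 14, window −3 to +7 days: day 11 to day 21 (1.6 to 3.0 weeks). The endpoint needs day 28 (4 weeks) and day 84 (12 weeks). Six months is about 26 weeks. The last dropout before the trigger may therefore have only 11 to 21 days of observation.

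**2. How many dropouts are short of follow-up at the trigger.** The documents do not give the enrolment period. Assumptions:
- Day 1 dates uniform over E weeks, with E from 13 to 52;
- dropouts' last doses uniform over weeks 0 to 22 after Day 1;
- last exit X weeks after the last Day 1, with X = 22 or 48 (the typical dosing range in the protocol synopsis).

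Follow-up at the trigger is F = a + b + (X − 22), with a uniform on (0, E) and b uniform on (0, 22).

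For X = 22:
- P(F < 12) = (12²/2)/(22E) = 72/(22E).
- P(F < 26) = 1 − (9²/2)/286 at E = 13, and (26²/2 − 4²/2)/(22E) = 330/(22E) for E ≥ 26.

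| E (weeks) | F < 12 weeks | F < 26 weeks |
|---|---|---|
| 13 | 72/286 = 25% | 86% |
| 26 | 72/572 = 13% | 58% |
| 39 | 72/858 = 8% | 38% |
| 52 | 72/1144 = 6% | 29% |

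For X = 48, F = a + b + 26, so every dropout has at least 26 weeks. That result depends on last doses falling by week 22. The last-enrolled subject stopping at week d has 48 − d weeks, which is under 12 if d exceeds 36.

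**3. Effect of the denominator.** Let N subjects have an event ongoing at last dose, let u be the share unresolved, and let k fall in one resolved row. With everyone kept, the row shows k/N. With unresolved subjects dropped as missing, it shows k/[N(1 − u)]. The ratio is 1/(1 − u):

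| u | Inflation |
|---|---|
| 10% | 1.11 |
| 20% | 1.25 |
| 30% | 1.43 |
| 40% | 1.67 |

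Under that reading the four rows sum to 100% whatever u is.

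**4. Scale, for illustration only.** In ARC001, 4 of 29 AR101 subjects (13.8%; exact 95% interval 3.9% to 31.7%) stopped for recurrent GI events. Applied to 500 × 2/3 = 333 AR101 subjects, this gives about 46 (range about 13 to 106). Suppose all 46 had an event ongoing at last dose, 14/8/10/4 fell in the four rows and 10 were followed and unresolved (an invented split). With denominator 46 the rows read 30.4/17.4/21.7/8.7%, plus 21.7% unresolved. With denominator 36 they read 38.9/22.2/27.8/11.1%.

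**The case against.** The other side has four good arguments.

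- **The trigger applies to the study.** A reader might infer from SAP 8 that each dropout's data are cut at the Early Discontinuation Visit. The text does not say so: it fixes when the analysis runs and states no per-subject cut-off. The SAP plainly expects later data, with rows beyond 4 weeks, weeks to resolution in the listing, and monthly PEESS summaries. Early dropouts will usually have long follow-up by then.
- **The denominator can be read more kindly.** A reader might also infer that the four rows must always total 100%. That follows only from the nonmissing default, which yields to other specification. SAP 4.2 can be read as counting all subjects who stop for these events, and 9.8.2 as counting all with ongoing events. An event recorded as ongoing is also arguably known status and not missing data.
- **Persistence shows elsewhere.** The listing in 9.8.2, the summary of subjects needing GI follow-up in 9.1 and the PEESS summaries would reveal it.
- **The study is descriptive.** No hypothesis test is affected.

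These arguments limit the point but do not remove it. Under the kinder denominators, unresolved subjects appear only as 100% minus the row total, mixed with those lost or still in follow-up. The other outputs do not supply the endpoint's percentage, and the protocol calls its use of PEESS exploratory. Protocol 9 says "The end of study is defined as the date of the last visit of the last subject", but not whether GI follow-up visits count, and SAP 8 ties the analysis to the earlier visit.

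**Conclusion.** The concern holds in a limited form. Three facts rest on the text alone: the table has only resolved rows, no denominator is fixed for it, and the final analysis does not wait for GI follow-up and has no stated cut-off or censoring rule.

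The size is conditional. Under the uniform-timing assumptions, 6% to 25% of dropouts would have under 12 weeks observed if the last exit is 22 weeks after the last Day 1, and none if it is 48 weeks. Inflation by 1/(1 − u) arises only if the nonmissing default is applied; u is unknown. The documents do not support saying that all dropouts are cut at 2 weeks or that unresolved harm is certain to vanish from the percentages. Nor should subjects not yet observed to 12 weeks be counted as unresolved: that gives only a lower bound on resolution.

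The SAP should be changed, because programming choices would otherwise decide what the endpoint reports.

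**What to change.** **SAP 9.8.2 (and 4.2).** Use as fixed denominator all subjects who stopped dosing for chronic or recurrent GI adverse events with an event ongoing at last dose. Keep the four resolved rows and add two:
- 'not resolved at last contact, ≥12 weeks observed';
- 'not resolved or unknown, <12 weeks observed'.

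Treat the second added row as censored, not as failure to resolve. Kaplan-Meier time to resolution, censored at last contact, is an option. State how a subject with several ongoing events is classified, since the protocol endpoint counts events and the SAP counts subjects.

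**SAP 8.** State the data cut-off. Make this table final only when each of these subjects has reached resolution or the end of the Protocol 7.3.4.2 follow-up. If the main analysis comes earlier, report the table at that cut-off and update this one table when follow-up ends.

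**Cost.** SAP wording and one re-run of a small table. No visits are added, because the protocol already requires the follow-up. The resolved percentages may look less favourable than under a nonmissing denominator.
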